1.0 OBJECTIVES

This is a randomized placebo-controlled Phase II study of irradiated, adenovirus vector transfected GM-CSF secreting autologous leukemia cell vaccination (GVAX) vs. placebo given early after allogeneic HSCT for advanced MDS or AML patients with active disease going into transplantation.

1.1 Study Design

GVAX vaccines will be generated by adenoviral vector mediated GM-CSF gene transfer into myeloblasts harvested from study subjects prior to admission for hematopoietic stem cell transplant Patients with Myelodysplastic syndromes (MDS) with excess marrow blasts or Acute myeloid leukemia (AML) not in remission are eligible. Leukemia cells will be harvested for vaccination generation after enrollment. Patients will be randomized (1:1) to GVAX versus placebo arm prior to The assignment of treatment arm will be blinded to the patients, treating transplant admission. physicians, nurses, research staff, and data assessors. Between the leukemia cell harvest and admission for allogeneic HSCT, patients are allowed to receive additional therapy (e.g. HMA therapy, chemotherapy etc.) at the discretion of the treating physician. Between day+30 to +60* after HSCT, patients with adequate hematologic recovery and no GVHD requiring systemic therapy will receive GVAX or placebo vaccine (normal saline) injections weekly x 3 week, then starting on week 5, every 2 weeks for 6 weeks, to complete a set of six total vaccinations. Patients will remain on tacrolimus for GVHD prevention during the vaccination period. Tacrolimus taper may commence after completion of vaccination, at the discretion of the treating physician, with the goal to be off immune suppression by 6-9 months post transplant in the absence of GVHD.

* Day 60 or next business day, if day 60 occurs on a weekend or holiday

1.2 **Primary Objective:**

Progression-free survival (PFS) at 18 months after randomization

1.3 Secondary Objectives:

- a) To assess the safety of vaccination following allogeneic (ablative or reduced intensity) stem cell transplantation
- b) To assess incidence of grade 2-4 and grade 3-4 acute GVHD, and chronic GVHD after vaccination following allogeneic stem cell transplantation.
- c) To assess PFS after start of vaccination
- d) To assess relapse and non-relapse mortality after vaccination
- e) To assess overall survival after vaccination
- f) To assess biologic activity of GVAX as compared to placebo vaccination after HSCT (see Section 8.0)

CONFIDENTIAL

2.0 BACKGROUND

2.1 Study Agent

GVAX vaccines will be generated by adenoviral vector mediated GM-CSF gene transfer into myeloblasts harvested from study subjects prior to admission for HSCT.

2.2 Study Disease: Allogeneic SCT for Advanced MDS/AML

Although allogeneic hematopoietic stem cell transplantation is a potential curative therapy for patients with advanced hematologic cancers, disease relapse remains the single most frequent cause of treatment failure. Success of allogeneic HSCT relies heavily on the development of anti-tumor activity generated by the new donor derived immune system post transplant, also known as the graft-versus-tumor effect (GVT). Attempts to enhance GVT by early withdrawal of immune suppression or administration of donor lymphocyte infusions (DLI) have been hampered by increased rates of graft-versus-host disease (GVHD). Strategies to safely inducing GVT without promoting GVHD are needed.

2.3 Rationale

The early post-transplant period after allogeneic HSCT provides an attractive platform for adoptive immunotherapy and cancer vaccination strategies that could elicit tumor specific responses from the resurging donor immune cells. Vaccination during the first 2 months after transplantation may further capitalize upon the lymphodepletion resulting from the conditioning chemotherapy, and take advantage of the homeostatic lymphoid expansion that occurs during this period. Indeed, our pilot study in patients with advanced MDS/AML (DFCI protocol 04-023), as described in section 2.4 below, demonstrated that vaccination with GVAX early after allogeneic HSCT is feasible, safe, and associated with very encouraging clinical outcomes with detectable immune responses.

To extend this effort, we propose a randomized placebo controlled trial investigating the efficacy of vaccination using GM-CSF transfected autologous leukemia cells (GVAX) in patients with advanced MDS or high risk AML early after allogeneic HSCT.

2.4 Correlative Studies Background

2.4.1 GM-CSF Based Tumor Vaccines (GVAX)

Several animal tumor models have demonstrated potent and specific anti-tumor immune responses with appropriate immune stimulation. The local release of immuno-modulatory cytokines has been shown to be a useful adjuvant to tumor cell-based vaccine strategies. This can be most effectively achieved by transfection of the cytokine gene into the tumor cell, which is then irradiated and injected into the animal as a tumor-specific vaccine. In one study in which over 10 cytokines were compared in poorly immunogenic murine tumors, GM-CSF was identified as the most potent cytokine capable of generating systemic immunity that was CD4+ and CD8+ T cell dependent.² This vaccine approach has been shown to protect and cure mice after challenge with various cancer cell lines, including AML,³ and suggests that it is effective in treating minimal disease states.

The use of GM-CSF as a vaccine adjuvant has been explored in several phase I clinical trials, in diseases such as AML, melanoma, hepatocellular carcinoma, pancreatic cancer, prostate cancer and renal cell carcinoma. These GM-CSF augmented vaccines were safe and well tolerated in patients. The vast majority of adverse events were grade 1-2 injection site reactions characterized by erythema, induration, tenderness and localized pruritis. Systemic adverse events have included generalized pruritis, rash, fatigue, fever, headache and malaise.

At DFCI, a series of vaccination studies using GM-CSF based vaccines have been performed. In one phase I clinical trial, irradiated autologous melanoma cells engineered by retroviral mediated gene transfer to secrete GM-CSF (GVAX) were used to vaccinate 21 patients with metastatic melanoma.⁷ In subsequent studies, irradiated autologous tumor cells engineered to secrete GM-CSF by adenoviral mediated gene transfer were administered by intradermal and subcutaneous injection at weekly and biweekly intervals in 34 patients with metastatic melanoma⁶ and 34 patients with metastatic lung cancer ⁵ (average GM-CSF secretion 745 ng/10⁶ cells/24 hours and 513 ng/10⁶ cells/24 hours, respectively). In each of these studies, a common feature was the development of intense localized skin reaction at the vaccine injection sites, associated with a dramatic influx of dendritic cells, macrophages, eosinophils and T lymphocytes which were not present prior to vaccination. These reactions were associated with subsequent immune mediated tumor rejection at distant metastatic sites. Collectively, these studies showed that local production of GM-CSF improves tumor antigen presentation by increasing the number and activity of professional antigen presenting cells in the tumor microenvironment. In the adenoviral melanoma trial, at a minimum follow up of 36 months, 10 patients are alive (29%) and 4 with NED.⁶ Studies to elucidate the targets of the immune response have provided evidence of the presence of a coordinated humoral and cellular response to disease specific antigens.^{8,9}

2.4.2 GVAX after Allogeneic HSCT for MDS/AML

We have previously completed a pilot clinical trial using AML-GVAX in patients with advanced MDS or refractory AML after allogeneic stem cell transplantation (DFCI protocol 04-023), the results of which have recently been published. In this study, patients with MDS-RAEB or AML not in remission who have a donor matched at HLA-A,B, and DRB1 were eligible. Leukemia blasts were collected for GVAX generation prior to start of conditioning. The preparative regimen consisted of fludarabine 30mg/m2/d IV x 4, and busulfan 0.8mg/kg IV q12H x 8 doses. G-CSF mobilized PBSC was infused on day 0. GVHD prophylaxis included tacrolimus starting day -3, and methotrexate 5 mg/m2 days 1,3,6,11. GM-CSF (Leukine) 250 mg/m2 SC QD was administered from day+1 until neutrophil engraftment. GVAX was initiated between day +30 to +45 if there was adequate hematologic count recovery and no grade II-IV acute GVHD. GVAX was administered weekly for the first three doses, and q2weeks for the last three doses. Taper of tacrolimus began after vaccine completion. Irradiated autologous tumor cell DTH were given pre and post vaccinations to assess immune responses.

A total of 24 patients were transplanted on this study (13 unrelated, 11 related donors). Vaccines were successfully produced for all subjects. The average GM-CSF secretion rate was 52 ng/10⁶ cells/24 hours. The average pre-freeze viability was 98%. Diseases included: AML (16), MDS/RAEB (6), CML myeloid blast crisis (2). Median age was 62 years (range, 41-71). All patients had active disease at the time of transplant admission. Median marrow blast content prior to HCT was 20% (range, 6-91%). Median vaccine cell dose was 1.0 x 10⁷ cells (range, 0.1-1.0 x10⁷). Nine patients did not initiate

vaccination because of rapidly progressive disease post-HCT (4), grade II-IV acute GVHD (3), sepsis (1), pneumonitis (1). Fifteen patients initiated vaccination. Ten patients completed all six vaccinations. 5 patients did not complete all vaccinations (progressive leukemia-3, appendicitis-1, and grade II skin acute GVHD-1). Two patients developed late acute GVHD in the setting of tacrolimus taper after all vaccinations were completed. No patient develop grade 3-4 GVHD. The cumulative incidence of grade 2 acute GVHD for vaccinated patients was 20%. Seven of 15 patients vaccinated developed chronic GVHD (6 mild, 1 moderate). All responded to corticosteroid therapy. The cumulative incidence of chronic GVHD was 47%. Among the 15 patients who started vaccination after transplant, 9 are alive and in complete remission with a median follow up of 45 months (range 33-63 months). Kaplan-Meier estimate for 2-yr overall survival (OS) for all vaccinated patients was 56 ± 14% (Figure 1). Nine of 10 patients who completed all 6 vaccines remain in complete remission with an estimated Kaplan-Meier overall survival of 88 + 12%.

[figure not shown]

Figure 1. Survival after RIC HCT for advanced AML and MDS. OS is displayed for all pts (blue line), those that received at least 1 vaccination (green line), and those that completed all vaccinations (red line).

To obtain a historical control cohort most comparable to patients who started vaccination in this trial, we analyzed our institutional data for contemporaneous patients aged >40 years undergoing RIC SCT between 2004-2007 with similar Bu/Flu conditioning for untreated

MDS RAEB or AML not in remission. We further restricted the population to those who did not develop grade II-IV GVHD before day+45, and who were alive at day +60 to render them most similar to patients on our trial who would have started GVAX. Using these criteria, we identified 34 patients (16 AML, 18 MDS RAEB) in the historical control group. The 2-year overall survival for this group of patients was 18% as compared to 56% among patients who received at least 1 vaccination in this study (DFS (18% vs. 56%, p = 0.02).

tumor destruction and decreases in the levels of circulating soluble MHC class I chain-related protein A (MICA).¹¹ MICA and the closely related MHC class I chain-related protein B (MICB) are ligands for NKG2D, an activating receptor expressed on NK cells and CD8⁺ T lymphocytes that contributes to antitumor cytotoxicity.¹² Tumor cells may escape from NKG2D mediated immune destruction through the shedding of surface MICA and possibly other ligands. Prior to vaccination, 13/15 patients had high levels of shed MICA and/or MICB. Six of 7 long-term responding subjects with detectable ligands showed marked decreases in response to therapy. In the 3 patients who achieved complete remissions following vaccination and tacrolimus withdrawal, the levels of soluble ligands closely mirrored the disease course. In contrast, patients who did not have sustained remissions failed to display persistent decreases in shed MICA and MICB. To determine whether declines in soluble NKG2D ligands are linked to clinical response, we examined serial serum samples obtained from 35 patients who maintained a complete remission after allo-HCT alone. Only a minority showed high pre-treatment levels of soluble MICA in a range similar to the vaccinated subjects, perhaps indicative of the advanced disease-risk status of the immunized patents. Nonetheless, none of the control subjects with high levels of shed MICA exhibited the marked decrease in ligands detected in the vaccinated patients.

We also investigated whether we could identify potential targets of vaccination post-HSCT. One target, protein disulfide isomerase (PDI) has been identified through screening a murine renal cell carcinoma cDNA expression library with sera from mice that received GVAX. ERp5, a closely related disulfide isomerase involved in MICA shedding, evokes potent humoral reactions in solid tumor patients who clinically respond to GM-CSF-secreting tumor cell vaccines. High titer antibodies to human PDI were similarly induced in an AML patient who achieved a complete response after post-HSCT vaccination. In addition, sera from 5 of 9 long term survivors recognize L1CAM (CD171), a surface protein overexpressed in a variety of tumors, where it promotes transformation through MAP kinase pathways. Monoclonal antibodies targeting L1CAM mediate tumor destruction in xenograft models. These

findings raise the possibility that vaccination-induced antibodies might mediate tumor eradication.

Given that all of the patients in this trial had active disease at the time of transplant and then received a reduced intensity conditioning regimen, we would have expected few to enter complete and sustained remission. These promising results suggest GVAX vaccination is safe and may have anticancer activity in patients with MDS/AML after allogeneic HSCT.

3.0 PARTICIPANT SELECTION

3.1 Eligibility Criteria

Participants must meet the following criteria on screening examination to be eligible to participate in the study:

- 3.1.1 AML, MDS-RAEB (including CMML with excess blasts and MDS/MPN overlap syndrome) not in remission (defined as ≥ 5% blast in bone marrow or peripheral blood) prior to leukemia cell harvest. Patients may receive additional cytoreductive therapy after leukemia cell harvest and before admission for transplant, at the discretion of the treating physician. For patients with MDS-EB1(<10%blasts) or CMML-1, it is recommended that they proceed directly to transplant after the harvest if donor is available. If there is an extended delay, interval therapy with HMA is allowed.
 - 3.1.1.1 Patients may or may not have active disease at the time of transplant conditioning, but for RIC candidates, it is strongly recommended that disease is cytoreduced such that the pre-transplant admission marrow shows:
 - <30% blasts in a normocellular marrow (>=50% cellularity), or
 - <50% blasts in a hypocellular marrow (<50% cellularity)
- 3.1.2 HLA 8/8 or 7/8 matched related or unrelated donor available, as determined by antigen or allele level typing at HLA A, B,C, and allele level typing at HLA DRB1.
- 3.1.3 ECOG performance status 0-2.
- 3.1.4 Age ≥18 years. Because no dosing or adverse event data exist on the use of GVAX in participants <18 years of age, children are excluded from this study.
- 3.1.5 Patient deemed to be suitable candidate for myeloablative or reduced intensity conditioning allogeneic HSCT using PBSC or marrow as stem cell source.
- 3.1.6 Participants must have normal organ function as defined below:

Total bilirubin $\leq 2.0 \text{ mg/dL}$

(In patients with Gilbert's Syndrome, Total Bilirubin ≥ 2.0 is permitted)

AST (SGOT)/ALT (SGPT) \leq 3 X institutional upper limit of normal Serum creatinine \leq 2.0 mg/dL

- 3.1.7 The effects of GVAX on the developing human fetus are unknown. For this reason, women of child-bearing potential and men must agree to use adequate contraception (hormonal or barrier method of birth control; abstinence) prior to study entry and for the duration of study participation. Should a woman become pregnant or suspect she is pregnant while participating in this study, she should inform her treating physician immediately.
- 3.1.8 Ability to understand and the willingness to sign a written informed consent document.

3.2 Exclusion Criteria

Participants who exhibit any of the following conditions at screening will not be eligible for admission into the study.

- 3.2.1 Leukemia with active CNS involvement
- 3.2.2 Positive HIV or HTLV-1 serology.
- 3.2.3 Participants may not be receiving any other Non-FDA approved study agents at the start of conditioning for stem cell transplantation. Patients may receive Non-FDA approved agents at the time of screening/enrollment as long as such agent(s) will be discontinued by the start of conditioning for transplantation.
- 3.2.4 History of allergic reactions attributed to compounds of similar chemical or biologic composition to GM-CSF.
- 3.2.5 Uncontrolled intercurrent illness including, but not limited to ongoing or active infection, symptomatic congestive heart failure, unstable angina pectoris, cardiac arrhythmia, or psychiatric illness/social situations that would limit compliance with study requirements.
- 3.2.6 Pregnant women are excluded from this study because pregnancy is an exclusion for chemotherapy and stem cell transplantation
- 3.2.7 Individuals with a history of a different malignancy are ineligible except for the following circumstances. Individuals with a history of other malignancies are eligible if they have been disease-free for at least 2 years. Individuals with the following cancers are eligible if diagnosed and treated within the past 2 years: cervical cancer *in situ*, and basal cell or squamous cell carcinoma of the skin.
- 3.2.8 Prior allogeneic transplant

3.3 Inclusion of Women, Minorities and Other Underrepresented Populations

This study will be open to all participants with AML/MDS, including women, minorities, and other underrepresented populations, as long as they meet the conditions of eligibility outlined above.

4.0 REGISTRATION PROCEDURES

4.1 General Guidelines for DF/HCC and DF/PCC Institutions

Institutions will register eligible participants with the DF/HCC Quality Assurance Office for Clinical Trials (QACT) central registration system. Registration must occur prior to the initiation of therapy. Any participant not registered to the protocol before treatment begins will be considered ineligible and registration will be denied.

A member of the study team will confirm eligibility criteria and complete the protocol-specific eligibility checklist.

Following registration, participants may begin protocol treatment. Issues that would cause treatment delays should be discussed with the Principal Investigator. If a participant does not receive protocol therapy following registration, the participant's protocol status must be changed. Notify the QACT Registrar of participant status changes as soon as possible.

4.2 Registration Process for DF/HCC and DF/PCC Institutions

The QACT registration staff is accessible on Monday through Friday, from 8:00 AM to 5:00 PM Eastern Standard Time. QACT does not randomize after hours. Subjects must be registered between 8 A.M. and 5 P.M. Monday – Friday.

The registration procedures are as follows:

- 1. Obtain written informed consent from the participant prior to the performance of any study related procedures or assessments.
- Complete the protocol-specific eligibility checklist using the eligibility assessment documented
 in the participant's medical/research record. To be eligible for registration to the study, the
 participant must meet each inclusion and exclusion criteria listed on the eligibility
 checklist.

Reminder: Confirm eligibility for ancillary studies at the same time as eligibility for the treatment study. Registration to both treatment and ancillary studies will not be completed if eligibility requirements are not met for all studies.

3. Fax the eligibility checklist(s) and all pages of the consent form(s) to the QACT at [contact].

- 4. The QACT Registrar will (a) validate eligibility, (b) register the participant on the study, and (c) randomize the participant.
- 5. The QACT Registrar will send an email confirmation of the registration to the person initiating the registration immediately following the registration. Randomization result/ study arm assignment will be emailed to Cell Manipulation Core Facility (CMCF). All other study personnel will remain blinded to the study arm assignment.

5.0 TREATMENT PLAN

- 5.1 Treatment can be administered on an either inpatient or outpatient basis. Expected toxicities and potential risks for irradiated, adenovirus vector transfected GM-CSF secreting autologous leukemia cell vaccination (GVAX) are described in Section 6 (Expected Toxicities and Dosing Delays/Dose Modification). No investigational or commercial agents or therapies other than those described below may be administered at the start of conditioning through vaccination with the intent to treat the participant's malignancy. Pre-treatment criteria/Pre-transplant
 - 5.1.1 **Pre-transplant evaluation**: All subjects enrolled on this study will undergo standard pre-transplant evaluation before the transplant date as required by Foundation for the Accreditation of Cellular Therapy (FACT) regulations and according the institutional standard operating procedure.
 - 5.1.2 **Randomization**: After enrollment, patients will be randomized in a 1:1 fashion to one of 2 arms on the study: "GVAX" vs. "Placebo". Randomization will be stratified by center (DFCI, BIDMC, MGH), disease, age (≥50 vs. <50), and conditioning intensity (myeloablative Flu/Bu4 vs. reduced intensity conditioning Flu/Bu2). Leukemia cell harvest will be performed on all patients regardless of their randomization status.
 - 5.1.3 **Leukemia cell harvest**: Blood for infectious disease marker (IDM) testing will be drawn prior to, or on the day of leukemia cell harvest. Leukemia cells for vaccine generation will be harvested via bone marrow aspiration and/or peripheral blood draw. Please note that the DFCI Cell Manipulation Core Facility can only accept collections Monday-Wednesday. The procedure for vaccine generation is detailed below:
 - 5.1.3.1 Bone marrow collection: 40 cc of marrow aspirate will be taken to collect leukemic blasts for vaccine generation and laboratory immune studies. If the patient's most recent marrow biopsy was performed within 2 weeks of the collection, an additional aspirate and core biopsy for routine clinical staging might be performed as a part of the marrow harvest at the discretion of the treating physician, and based on standard clinical practice.
 - 5.1.3.2 Peripheral blood draw: If the patient has blasts in peripheral blood, tumor cells may be collected by blood draw. The amount of blood required may vary depending on calculations of blood volume needed to yield a desired target of 2 x 10^7 leukemia cells. If the calculated volume of blood draw exceeds 50 ml, it is recommended that bone marrow aspiration be used as the method for tumor cell harvest.
 - 5.1.3.3 Leukapheresis: In cases where peripheral blood draw and/or marrow harvest is infeasible or unsuccessful, and the patient has circulating blasts, a single leukapheresis may be

performed to harvest leukemia blasts. The leukapheresis collection will follow standard institutional leukapheresis guidelines.

- 5.1.3.4 Multiple harvests: If the first attempt to collect sufficient cells to generate six vaccines is insufficient, a second harvest may be performed. If the second harvest is insufficient, the participant will be taken "off-study."
- 5.1.3.5 All leukemia cells harvested through bone marrow aspiration and/or peripheral blood and/or leukapheresis draw will be sent to DFCI for vaccine/placebo preparation.
- 5.1.4 **Vaccine preparation**: For study participants randomized to the GVAX arm, autologous myeloblasts will be introduced into short-term tumor culture in the presence of G-CSF, and transduced with a replication defective adenoviral vector encoding human GM-CSF.

After transduction, the tumor cells will be washed extensively and irradiated with 10,000 cGy. A small aliquot of the transduced cells will be placed into culture and GM-CSF secretion will be determined by ELISA. The target level for GM-CSF production will be at least 40 ng/10⁶ cells/24 hours, although achieving this secretion will not be required for vaccine administration. Routine sterility cultures and testing for endotoxin and mycoplasma contamination will be performed.

Tumor cells for vaccination and immunologic evaluation will be cryopreserved and stored in the vapor phase of liquid nitrogen. Six individual vaccine aliquots will be prepared for each patient. Cell dose per aliquot will be fixed for an individual patient and will range from about $1x10^6$ cells per aliquot to $1x10^7$ cells per aliquot. The exact vaccine cell dose in each patient will vary depending on the total yield of myeloblasts harvested. The dosage will be determined by dividing the total cell yield following transduction into six aliquots. For total cell yields greater than $6x10^7$, individual aliquots will remain at a maximum of $1x10^7$ cells per dose. Thus, vaccine cell dosage will vary depending on the final vaccine cell yield after processing. This variation in cell dosage is designed to maximize each patient's opportunity of receiving vaccinations and is not based on any expectation of significant differences in toxicity as a function of cell number. On the day of vaccine administration, cells will be thawed in a dedicated laminar flow biosafety cabinet in the CMCF and washed. Cells will be re-suspended in a volume of 1 ml. for administration via a masked syringe

Details of the construction of the adenoviral producer cell line and safety tests on this line are included in the Appendix (vector manufacturing process). The adenoviral vector was manufactured by Cell Genesys and approved for clinical use by the Food and Drug Administration.

- 5.1.5 **Placebo Vaccine Preparation**: The placebo vaccine will be composed of 1 ml sterile Normal Saline in a masked syringe. The vaccine will be thawed, and the thawed placebo/vaccine will be drawn into a masked syringe at DFCI to protect blinding. The syringe will then be released for administration
- 5.1.6 **Cytoreductive therapy between harvest and HSCT**: Patients may receive additional cytoreductive therapy after leukemia cell harvest and before admission for transplant, at the discretion of the treating physician. For patients with MDS-RAEB1, it is recommended that they proceed directly to transplant after the harvest if donor is available. If there is an extended delay,

interval therapy with HMA is allowed.

- 5.1.6.1 Patients may or may not have active disease at the time of transplant conditioning, but for RIC candidates, it is strongly recommended that disease is cytoreduced such that the pre-transplant admission marrow shows:
 - <30% blasts in a normocellular marrow (>=50% cellularity), or
 - <50% blasts in a hypocellular marrow (<50% cellularity)

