7.1.3 Storage and Stability

Tumor cells for vaccination and immunologic evaluation will be cryopreserved and stored in liquid nitrogen. Six individual vaccine aliquots will be prepared for each patient. Cell dose per aliquot will be fixed for an individual patient and will range from a minimum of $1x10^6$ cells per aliquot to $1x10^7$ cells per aliquot. The dosage will be determined by dividing the total cell yield following transduction into six aliquots. Thus, a minimum of $6x10^6$ cells will be required to

prepare six aliquots of $1x10^6$ cells. For total cell yields greater than $6x10^7$, individual aliquots will remain at $1x10^7$ cells per dose.

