7.1.6 Preparation

7.1.6.1 GVAX

Harvested autologous myeloblasts will be transferred to the Cell Manipulation Core Facility (CMCF) at the Dana Farber Cancer Institute. The autologous myeloblasts will be introduced into short-term tumor culture in the presence of G-CSF, and transduced with a replication defective adenoviral vector encoding human GM-CSF.

After transduction, the tumor cells will be washed extensively and irradiated with 10,000 cGy. A radiation indicator tag that changes color from red to black after radiation will be appended to the bag containing the cells to assure that radiation is completed. In addition, the completion of radiation will recorded by 2 qualified members of the laboratory, who will also verify that the appropriate radiation dose of 10,000 cGy is delivered.

A small aliquot of the transduced cells will be placed into culture and GM-CSF secretion will be determined by ELISA. The target level for GM-CSF production will be at least 40 ng/10⁶ cells/24 hours, although achieving this secretion will not be required for vaccine administration. Routine sterility cultures and testing for endotoxin and mycoplasma contamination will be performed.

Tumor cells for vaccination and immunologic evaluation will be cryopreserved and stored in liquid nitrogen. Six individual vaccine aliquots will be prepared for each patient. Cell dose per aliquot will be fixed for an individual patient and will range from about $1x10^6$ cells per aliquot to $1x10^7$ cells per aliquot. The exact vaccine cell dose in each patient will vary depending on the total yield of myeloblasts harvested. Vaccine dose will be calculated based on the myeloblast count performed on a post-ficoll sample assessed in the Hematology Laboratory at DFCI. Following transduction, the final product will be divided equally into six aliquots to yield 6 vaccines of the same dose. For total cell yields greater than $6x10^7$, individual aliquots will remain at a maximum of $1x10^7$ cells per dose.

On the day of vaccination, cells will be thawed in a dedicated laminar flow biosafety cabinet in the CMCF and washed. Cells will be re-suspended in a volume of 1 ml. in a syringe for administration. The syringe will be masked with special tape to prevent administrating personnel from distinguishing cellular vaccines from placebo.

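### A GVAX patient fit to start but with no releasable product is dropped from the primary analysis, which saline cannot cause; define the analysis set by the start criteria instead (minor, cheap to fix)

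*Combined protocol and SAP*

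**What the plan says.** Randomization takes place at registration (Section 4.2). The harvest follows, in both arms (Section 5.1.2).

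On shortage of cells, Section 5.1.3.4 says "If the first attempt to collect sufficient cells to generate six vaccines is insufficient, a second harvest may be performed". It continues "If the second harvest is insufficient, the participant will be taken" off-study. The wording covers all participants and refers to collected cells, and it gives no count.

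Manufacture then differs by arm:

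- **GVAX.** Section 5.1.4: "For study participants randomized to the GVAX arm, autologous myeloblasts will be introduced into short-term tumor culture" and then transduced. "Routine sterility cultures and testing for endotoxin and mycoplasma contamination will be performed". On dose, Section 7.1.3 says "The dosage will be determined by dividing the total cell yield following transduction into six aliquots", from which it derives that "a minimum of $6x10^6$ cells will be required" for six aliquots. Sections 5.1.4 and 7.1.6.1 soften the floor to about 1x10^6 cells per aliquot. Low GM-CSF secretion does not block dosing.
- **Placebo.** Saline prepared on the day of vaccination (Section 7.1.6.2). It needs no cells.

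The protocol does not say what happens when a GVAX product falls short or fails a release test. Two general rules then apply. Section 5.7 removes from study any participant who has not started vaccination by day +60. Section 12.1.1 restricts the primary analysis to transplanted, eligible patients who received at least one vaccination. The 30% attrition in Section 12.3 is attributed wholly to the clinical start criteria of Section 5.3.1.

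**The concern.** A modified intention-to-treat set that depends on an event after randomization is tolerable when the event has the same chance and meaning in both arms. The Section 5.3.1 criteria fit that description: they are clinical, applied under blinding, and precede any injection. Receiving a first injection does not quite fit. For GVAX it requires the start criteria and a usable cell product; for placebo it requires the start criteria alone.

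Take two patients who both meet Section 5.3.1 on day +40. One is on GVAX and the product has failed. The other is on placebo and, had the assignment been GVAX, would also have had a failed product. The first is removed and not analysed; the second is injected and analysed. Cell dose depends on the myeloblasts harvested (Section 5.1.4), so patients without product may differ in disease burden. The PFS comparison would then not be strictly between randomized groups.

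**Working it through.** **1. The plan's own figures.** Equations (1) and (2) of Section 12.5 give S_A(18) = 0.4593 and S_B(18) = 0.2615, a gain of 19.8 points, matching 46% against 26%. Enrolment is 106/0.7 = 151.4, so 152. A simulated one-sided 0.15 log-rank test, with 53 per arm, uniform accrual over 45.6 months (assumed) and 18 months of further follow-up, gives power 0.81 with 69.2 events. The plan states about 80% and 69. The sample size arithmetic is sound.

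**2. How often product could fail.** The only data are 0 of 24 in the pilot (Section 2.4.2).

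- Jeffreys estimate, Beta(0.5, 24.5): mean 0.5/25 = 2.0%, median 0.9%.
- One-sided 95% upper limit: 1 - 0.05^(1/24) = 11.7%.
- Of 53 GVAX patients able to start: 0.02 x 53 = 1.1; 0.05 x 53 = 2.7; 0.117 x 53 = 6.2.

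The pilot's median dose was at the 1x10^7 cap; its lowest was 1x10^6. The blood-draw target in Section 5.1.3.2 ("desired target of 2 x 10^7 leukemia cells") leaves less margin: it falls below the Section 7.1.3 minimum if recovery is under 6x10^6/2x10^7 = 30%. Recovery is not given, and this assumes no growth in culture.

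**3. Effect on the comparison with no true treatment effect.** Let f be the failure rate among GVAX patients able to start, and p the 18-month PFS of those dropped. Neither is in the documents; p is taken as 10% to 50%, around the 26% average. With accrual continued to 106 vaccinated, n_GVAX = 106(1-f)/(2-f) and n_placebo = 106/(2-f). The GVAX arm's PFS shifts by (0.2615 - f p)/(1 - f) - 0.2615.

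| f | GVAX vs placebo | Shift, p = 10% / 50% (points) | Type I, 18-month normal approximation | Type I, log-rank simulation |
|---|---|---|---|---|
| 0 | 53 vs 53 | 0 | 0.150 | 0.149 |
| 2% | 52.5 vs 53.5 | +0.33 / -0.49 | 0.159 / 0.137 | 0.161 / 0.139 |
| 5% | 51.6 vs 54.4 | +0.85 / -1.26 | 0.174 / 0.118 | 0.173 / 0.120 |
| 11.7% | 49.7 vs 56.3 | +2.14 / -3.16 | 0.216 / 0.080 | 0.211 / 0.078 |

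Example at f = 2%, p = 10%: (0.2615 - 0.0020)/0.98 = 0.2648, a shift of +0.33 points. The standard error of the difference is sqrt(0.2615 x 0.7385 x (1/52.5 + 1/53.5)) = 8.5 points. If p = 26%, the shift is zero.

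**4. Cost of keeping them.** If a fraction f of the GVAX arm follows S_B, the gain is 19.78(1 - f): 19.4, 18.8 and 17.5 points at 2%, 5% and 11.7%. Simulated power (20,000 runs) is 0.814 at f = 0, then 0.802, 0.787 and 0.746.

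**The case against.** The case for leaving the plan alone is substantial. No product failure is on record, and the floor of about 1x10^6 per aliquot is flexible; Section 5.1.4 says dose is allowed to vary so that as many patients as possible can be vaccinated. No section states that a failed release test removes a patient; that follows only from combining Sections 5.7 and 12.1.1. A vaccinated-only set is a declared choice in a phase II comparison that Section 12.5 itself calls nondefinitive. An all-randomized sensitivity analysis with failures reported by arm would cost less.

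Most of this stands and limits the point to a minor one. It does not remove it: no other section keeps such a patient in the primary analysis, and a sensitivity analysis leaves the primary set dependent on product.

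A reader might also infer that harvests will be judged sufficient or not according to arm, since Section 5.1.3.4 gives no number, the only stated minimum is a post-transduction one, and the cell facility knows the assignment. The documents do not support that. Section 5.1.3.4 is worded for every participant and for collected cells, and Section 7.1.6.1 already has a pre-transduction measure: "Vaccine dose will be calculated based on the myeloblast count performed on a post-ficoll sample assessed in the Hematology Laboratory at DFCI". A numeric definition of a sufficient harvest would be a clarification, not the correction of a shown asymmetry.

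**Conclusion.** The point holds in a narrow form. Under Sections 5.7 and 12.1.1 together, a randomized GVAX patient who meets the start criteria but has no product leaves the primary analysis, and failure of yield or transduction cannot do this to a placebo patient.

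The likely size is small and may be nil. At 2% failure the distortion is under half a point of 18-month PFS, against a standard error of 8.5 points. Type I error moves by about 0.01 at 2% and by up to 0.03 at 5%. The range of 0.08 to about 0.21 at 11.7% needs the upper confidence limit of a rate observed as zero together with an extreme assumed prognosis, so it is a bound and not an expectation.

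A reader might infer that the exclusion favours GVAX because poor harvests mean poor prognosis. The documents do not establish this: the sign depends on the PFS of those dropped, which is unknown, and average prognosis gives no bias.

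**What to change.** - **Section 12.1.1:** define the primary set as transplanted, eligible patients who meet the Section 5.3.1 criteria by day +60, analysed as randomized whether or not product was available. Sections 12.2 and 12.3 already count the 106 as patients eligible to start.
- **Section 5.7:** exempt patients without product from removal and keep them in PFS follow-up. Section 11.1.2 already collects transplant data on everyone enrolled.
- **Blinding:** the cell facility tells the site that there is no product only after the Section 5.3.1 assessment is recorded.
- **Reporting:** give harvest and product failures by arm.

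The cost is wording plus two downsides: slight dilution (power 0.81 to about 0.80 at 2% failure and 0.79 at 5%), and possible unblinding of a GVAX patient who turns out to have no product. These changes should be settled before unblinding.

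A new numeric harvest threshold is not needed for this. It would require a recovery fraction that the documents do not give, and could send off-study some patients whom the present minimum would allow to be vaccinated. Second harvests after poor transduction should not be barred either. Stating in Section 5.1.3.4 what count makes a harvest sufficient would be a useful clarification only.
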